1.3. Populations for Analyses

The following populations are defined:

Population	Description
Study participants with data in CRF Error! No document variable supplied.	All study participants included in the table shells are study participants with a Case Report Form (CRF) (i.e., with data in the clinical database).
Safety Analysis Set (SafAS)	
SafAS 1: Participants who have received the study vaccine 5 years after priming vaccination (at V1) and have any safety data available (Group 1).
 
SafAS 2: Participants who have received the study vaccine 10 years after priming vaccination at V3 (Group 1) / V2 (Group 2) and have any safety data available.
 
SafAS: Participants who have received at least one dose of the study vaccine. All participants will have their safety analyzed after any dose according to the vaccine received at the 1st dose.
 
All participants will have their safety analyzed according to the vaccine scheme they actually received.
 
Safety data recorded for a vaccine received out of the protocol design will be excluded from the analysis (and listed separately).

Full analysis set (FAS)	
The FAS will be duplicated for each FAS defined below: 1 each for hSBA and rSBA measurements.
 
FAS1: Subset of participants who received the study vaccine and had a valid post-vaccination serology result (hSBA or rSBA accordingly) 5 years after priming vaccination at V1 (Group 1). Participants will be analyzed according to the intervention they received.
 
FAS2: Subset of participants who received the study vaccine and had a valid post-vaccination serology result (hSBA or rSBA accordingly) 10 years after priming vaccination at V3 (Group 1) / V2 (Group 2). Participants will be analyzed according to the intervention they received.
 
FAS3: For persistence includes participants who had a valid baseline serology result (hSBA or rSBA accordingly) (5-year antibody persistence, Group 1 and Group 2)
 
FAS4: For persistence includes participants who had a valid pre-vaccination serology result (hSBA or rSBA accordingly) (5-

	
year antibody persistence after the first booster dose in Group 1, 10-year antibody persistence in Group 2). Participants will be analyzed according to the intervention they received.


PPAS
	
The PPAS will be duplicated for each PPAS defined below: 1 each for hSBA and rSBA measurements.
 
The PPAS is a subset of the FAS. PPAS1 and PPAS2 will be defined: PPAS1 for Group 1 V1, and PPAS2 for Group 1 and Group 2 at V3 and V2, respectively. Participants presenting with at least 1 of the following relevant protocol deviations will be excluded from the PPAS1 or PPAS2 as applicable.
 
 • Participant did not meet all protocol-specified inclusion criteria or met at least one of the protocol-specified exclusion criteria • Participant did not receive vaccine • Participant received a vaccine other than MenACYW conjugate vaccine • Preparation and/or administration of vaccine was not done as per-protocol • Participant did not receive vaccine in the proper time window • Participant did not provide post-dose serology sample in the proper time window or a post-dose serology sample was not drawn • Participant received a protocol-prohibited Category 2 or Category 3 therapy/medication/vaccine • Participant’s serology sample did not produce a valid test result (ie, results for all meningococcal antigens are missing) • Participant had other protocol deviations that affected the participant’s immune response, as determined by the clinical team before locking the database

Safety analyses after MenACYW conjugate vaccine received at V01 in Group 1 will be performed on SafAS 1. Safety analyses after MenACYW conjugate vaccine received at V03 in Group 1 and at V02 in Group 2 will be performed on SafAS2.

Immunogenicity analyses will be performed on:

- PPAS1 for the description of immune response to the MenACYW conjugate vaccination received at V01 in Group 1, and on FAS1 if the attrition rate from FAS1 to PPAS1 is greater than 10%.

- FAS3 for the persistence assessment in participants receiving approximately 5 years earlier as toddlers (Groups 1 and 2)
- PPAS2 for the description of immune response to the MenACYW conjugate vaccination received at V03 in Group 1 and at V02 in Group 2, , and on FAS2 if the attrition rate from FAS2 to PPAS2 is greater than 10%.
- FAS4 for the 5-year antibody persistence after the first booster dose in Group 1, and for the 10-year antibody persistence in Group 2. Group 1 and Group 2 will be described separately.

When applicable, the above populations will be duplicated for hSBA and rSBA measurements.

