5.4 Screen Failures

Screen failures are defined as participants who consent to participate in the clinical study but are not subsequently enrolled. Screening information is recorded in the source documents.

Individuals who do not meet the criteria for participation in this study (screen failure) can be rescreened when the condition excluding them from participation is resolved (eg, fever, antibiotics received within 72 hours, etc).

6 Study Intervention

Study intervention is defined as any investigational intervention(s), marketed product(s), placebo, or medical device(s) intended to be administered to a study participant according to the study protocol.

Note: routine vaccines administered outside of study protocol are not considered as study interventions.

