9.3 Populations for Analyses

The following populations are defined:

Population	Description
Safety Analysis Set (SafAS)	
 • SafAS 1: Participants who have received the study vaccine 5 years after priming vaccination (at V1) and have any safety data available (Group 1). • SafAS 2: Participants who have received the study vaccine 10 years after priming vaccination at V3 (Group 1) / V2 (Group 2) and have any safety data available. 
All participants will have their safety analyzed according to the vaccine they actually received.
 
Safety data recorded for a vaccine received out of the protocol design will be excluded from the analysis (and listed separately).

Full analysis set (FAS)	
The FAS will be duplicated for each FAS defined below: 1 each for hSBA and rSBA measurements.
 
 • FAS1: Subset of participants who received the study vaccine and had a valid post-vaccination serology result 5 years after priming vaccination at V1 (Group 1). Participants will be analyzed according to the intervention they received. • FAS2: Subset of participants who received the study vaccine and had a valid post-vaccination serology result 10 years after priming vaccination at V3 (Group 1) / V2 (Group 2). Participants will be analyzed according to the intervention they received. • FAS3: For persistence includes participants who have a valid serology result for at least 1 serogroup from a pre-vaccination blood sample (5-year antibody persistence, Group 1 and Group 2) • FAS4: For persistence includes participants who have a valid serology result for at least 1 serogroup from a pre-vaccination blood sample (10-year antibody persistence, Group 1 and Group 2)
PPAS	
The PPAS will be duplicated for each PPAS defined below: 1 each for hSBA and rSBA measurements.
 
The PPAS is a subset of the FAS. PPAS1 and PPAS2 will be defined: PPAS1 for Group 1 V1, and PPAS2 for Group 1 and Group 2 V3 and V2, respectively. Participants presenting with at

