9.4.1 General Considerations

All immunogenicity analyses will be performed on the PPAS and on the FAS. All safety analyses will be performed on the SafAS.

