1.4.3. Secondary Endpoints

Immunogenicity

All analyses for the secondary endpoints will be descriptive; no hypotheses will be tested. Descriptive statistics will be provided for the hSBA and rSBA antibody titers against meningococcal serogroups (A, C, W, and Y) and for antibody concentrations against tetanus toxoid contained in MenACYW conjugate vaccine as a carrier protein. The results will be expressed as vaccine seroresponse, seroprotection, GMTs, and titers greater or equal to a specific threshold.

In general, categorical variables will be summarized and presented by frequency counts, proportion percentages, and CIs. The 95% CIs of point estimates will be calculated using the normal approximation for quantitative data and the exact binomial distribution (Clopper-Pearson

method) for percentages. For GMTs, 95% CIs of point estimates will be calculated using normal approximation assuming they are log-normally distributed.

Reverse cumulative distribution curve (RCDC) figures will be provided for the antibody titers against meningococcal serogroups and the antibody concentrations against tetanus toxoid contained in MenACYW conjugate vaccine.

In summary, descriptive analyses of antibody responses to A, C, W, and Y serogroups for Group 1 (at V1 [baseline], V2 [30 days after the administration of a booster dose of MenACYW conjugate vaccine], and at V3 before the administration of a booster dose), V4 (30 days after the administration of a booster dose of MenACYW conjugate vaccine), and for Group 2 at V2 before the administration of a booster dose of MenACYW conjugate vaccine and at V3 (30 days after the administration of a booster dose of MenACYW conjugate vaccine) will include but not be limited to:

- hSBA and rSBA seroprotection rate (titer \geq 1:8) and 95% CI
- hSBA and rSBA GMTs and 95% CI
- hSBA and rSBA titer distribution and RCDC
- Percentage of participants with hSBA titer \geq 1:4 and \geq 1:8 and 95% CI
- Percentage of participants with rSBA titer \geq 1:8 and \geq 1:128 and 95% CI
- Percentage of participants with hSBA and rSBA titer \geq 4-fold rise from pre-vaccination to post-vaccination, and 95% CI
- Percentage of participants with hSBA and rSBA vaccine seroresponse rate and 95% CI

hSBA vaccine seroresponse for serogroups A, C, W, and Y is defined as:

- For a participant with a pre-vaccination titer $<$ 1:8, the post-vaccination titer must be \geq 1:16

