1.8.5.5. MenC primed status

Participants who have received monovalent MenC vaccination during infancy are considered as “Primed” whereas participants who haven’t received monovalent MenC vaccination during infancy is considered as “Naïve”. The MenC primed status is defined according to the priming status in infancy before receiving the toddler dose in MET51 study

5. Changes in the Conduct of the Trial or Planned Analyses

Not applicable.

6. Supporting Documentation

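### SAP 1.3 gives Year 5 persistence to FAS4 alone, and FAS4 as worded does not exclude titers taken after a non-study meningococcal vaccine; a restricted analysis beside it would be a cheap improvement

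*SAP*

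**What the plan says.** SAP 1.3 (Populations for Analyses) defines the set by "FAS4: For persistence includes participants who had a valid pre-vaccination serology result (hSBA or rSBA accordingly" and adds that participants are analyzed by the intervention received. The assignment is explicit: "FAS4 for the 5-year antibody persistence after the first booster dose in Group 1, and for the 10-year antibody persistence in Group 2". The response to the Year 5 dose goes elsewhere: "PPAS2 for the description of immune response to the MenACYW conjugate vaccination received at V03 in Group 1 and at V02 in Group 2". The exclusions for protocol deviations, including receipt of another vaccine, are listed for PPAS1 and PPAS2 only.

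Protocol 9.4.1 states a broader rule: "All immunogenicity analyses will be performed on the PPAS and on the FAS". SAP 1.3 does not apply it to persistence, and SAP section 5, "Changes in the Conduct of the Trial or Planned Analyses", is marked not applicable.

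On outside vaccination, exclusion criterion E02 bars non-study A, C, W or Y vaccines at V1, apart from MenC vaccination in infancy. After V1 the same exposure is a definitive contraindication (DCI06, protocol 7.1.3). It stops further study doses but not immunogenicity follow-up. Section 7.1.3 also says that a vaccine given through a local or national programme does not lead to withdrawal. Protocol section 8 asks all participants for the Year 5 blood sample.

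**The concern.** The objectives are persistence after the MET51 dose (Group 2) and after the first booster (Group 1). A titer raised by another vaccine in between measures neither. The sample taken 5 years after the toddler dose (V1, FAS3) is protected by E02. The Year 5 sample has no matching rule, yet it feeds the paired 5- and 10-year trends in SAP 1.4.3. If outside vaccination were common, those trends would show less waning than the study doses alone would produce.

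Exposure is plausible from the protocol itself. Section 2.2 says several EU countries have introduced or are considering the quadrivalent vaccine, mainly as adolescent boosters, and section 10.1.3 puts participants at about 11 to 12 years at Year 5. No study country is named in that statement and no uptake is given.

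**Working it through.** **Does FAS4 admit these titers?**
- FAS1 and FAS2 require receipt of the study vaccine. FAS4 requires only a valid pre-vaccination result.
- The clause on intervention received does not separate these participants, because protocol section 6 says "routine vaccines administered outside of study protocol are not considered as study interventions".
- SAP 1.4.4.2 (missing immunogenicity data) adds no exclusion.
- The word *pre-vaccination* can be read two ways. The SAP uses *baseline* for FAS3 and *pre-vaccination* for FAS4, which suggests that FAS4 may be meant for participants then dosed at Year 5. On that reading DCI06 removes identified cases. Against it, the protocol's own FAS3, "FAS3: For persistence includes participants who have a valid serology result for at least 1 serogroup from a pre-vaccination blood sample", uses the word for Group 2 at V1, where no dose is given. On either reading, a participant whose outside dose goes unnoticed stays in.

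**How large could the effect be?** The plan gives no figure to reproduce here; its sample size calculation concerns the primary objective only. All inputs are therefore assumed, except n = 250, the stated maximum per group.
- f = share of FAS4 vaccinated elsewhere since V1; p = true seroprotection (hSBA ≥ 1:8) without that vaccine; q = seroprotection among those vaccinated elsewhere.
- Shift = f × (q − p).
- Coverage = probability that the Clopper-Pearson 95% interval contains p when the count is binomial with n = 250 and probability (1 − f)p + fq. For p = 50% the interval contains p when the count is 110 to 140.

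The value q = 99% is close to a ceiling. An outside dose may precede the sample by up to five years, so 80% and 70% are shown as waning cases.

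| p | f | q | Shift (points) | Coverage |
|---|---|---|---|---|
| 50% | 10% | 99% | 0.10 × 49 = 4.9 | 66% |
| 50% | 10% | 80% | 0.10 × 30 = 3.0 | 84% |
| 50% | 10% | 70% | 0.10 × 20 = 2.0 | 90% |
| 50% | 20% | 99% | 0.20 × 49 = 9.8 | 12% |
| 50% | 20% | 80% | 0.20 × 30 = 6.0 | 52% |
| 50% | 20% | 70% | 0.20 × 20 = 4.0 | 76% |
| 70% | 20% | 99% | 0.20 × 29 = 5.8 | 50% |
| 70% | 20% | 80% | 0.20 × 10 = 2.0 | 91% |

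For scale, the 95% half-width at n = 250 is 6.4 points at 50% and 5.9 at 70%. At f = 0 there is no bias.

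A GMT is multiplied by r^f, where r is the assumed titer ratio. For r = 4 the multiplier is 1.15 at f = 10% and 1.32 at f = 20%; for r = 10 it is 1.26 and 1.58.

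**The case against.** The best reply is that a nearly equivalent restricted estimate is already planned. SAP 1.4.3 tabulates titers before the Year 5 booster in both groups (for instance "for Group 2 at V2 before the administration of a booster dose of MenACYW conjugate vaccine"), and the booster response is analyzed on PPAS2. That set drops participants who were not dosed, those given another vaccine, and those with other deviations affecting the immune response. For identified cases it removes the same people. This largely stands. PPAS2 also loses participants without a valid, timely post-dose sample or with unrelated deviations, and SAP 1.3 does not assign persistence to it. A reader might infer that the plan has no protection at all; the documents do not support that.

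Second, the SAP's contrast between *baseline* and *pre-vaccination* favors the benign reading of FAS4. This stands as a real ambiguity, but the definition does not settle it.

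Third, an all-comers set is a legitimate description, and excluding on an event after enrollment can introduce selection. This also stands, and is why the restricted analysis should sit beside FAS4 and not replace it.

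A reader might also infer that the exposure cannot be traced. That goes too far. The contraindication review is entered in the CRF at Year 5 in both groups, and Table 1.2 ticks reportable concomitant medications at V1, V2 and V3, and medical history again at Year 5, in Group 2. However, protocol 6.5 starts source collection at first vaccination, which for Group 2 is Year 5, and its case report book window for other vaccines is about 28 days around the study dose.

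**Conclusion.** The point holds as a minor one. FAS4 as worded does not exclude Year 5 titers taken after a non-study A, C, W or Y vaccine, and SAP 1.3 names no other set for persistence. A reader might conclude that the persistence results will be biased or waning understated; the documents do not show that, because they give neither uptake nor Year 5 titers. Any bias would be expected to be upward, on the assumption that the outside vaccine leaves titers higher than they would otherwise be. Under the assumed inputs above, the shift runs from zero at no uptake to 9.8 points at 20% uptake with near-complete seroprotection, and it shrinks quickly if the outside dose has waned or true persistence is high. The endpoints are secondary and descriptive. The primary objective, tested in Group 1 from V1 to V2, is unaffected.

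**What to change.** 1. In SAP 1.3, beside all-comers FAS4, add a Year 5 persistence analysis, including the paired trends, that excludes titers for any serogroup contained in a non-study meningococcal vaccine received between V1 and the Year 5 sample. A MenC-only dose then removes the C titer and leaves A, W and Y. Report numbers excluded by group and country, and base statements about persistence of the study dose on this analysis.
2. State in FAS4 whether the Year 5 sample of a participant not dosed at Year 5 counts as pre-vaccination. Reconcile protocol 9.4.1 with SAP 1.3 on the sets used for persistence.
3. Identify exposure from records already collected: the Year 5 contraindication review, reportable concomitant medications, and source records. Reconcile Table 1.2 with protocol 6.5 on when medication collection starts in Group 2. The documents do not show that product and date are captured; where they are unknown, exclude all four serogroups.

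The cost is a short SAP revision and one extra table set. Precision falls slightly: at 50% seroprotection the half-width goes from 6.4 points (n = 250) to 6.7 with 10% excluded (n = 225) and 7.1 with 20% excluded (n = 200). Selection is possible: if those vaccinated elsewhere would otherwise differ by d points, the restricted estimate shifts by f × d, so 1 to 2 points for d = 10 to 20 at 10% uptake and 2 to 4 at 20%. Side-by-side tables show the loss of numbers and let the two estimates be compared.

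Separately, DCI06 read literally also covers Group 1's own first booster and so conflicts with the planned second one. That belongs in its own finding, and those passages must be reconciled.

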6.3.2 Blinding and Code-breaking Procedures

This is an open-label study.

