1.2. Sample Size Determination

All available and eligible participants, who participated in and completed the MET51 study (Groups 1 and 3) and received MenACYW conjugate vaccine as a part of the study, can be enrolled (approximately 500 participants), with approximately 250 participants each in MEQ00073 Group 1 and Group 2 (maximum estimate).

A sample size of 84 achieves at least 90.0% power to detect that the lower bound of the 1-sided 97.5% CI is greater than 0.75 (proportion under the null hypothesis) for the vaccine seroresponse to each serogroup using a 1-sided exact test with a significance level (alpha) of 0.025.

Table 3.1: Power of the study based on the primary objective

Antigen	Endpoint	Estimates* for MenACYW	Power (%)
A	Seroresponse	0.95	> 99.9
C	Seroresponse	0.90	92.6
Y	Seroresponse	0.95	> 99.9
W	Seroresponse	0.925	99.0
Global Power			> 90

*Estimated responses are based on the results of MET62 Group 1 that received 1 dose of MenACYW conjugate vaccine (estimates of MET62 minus 5%).

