1.4.2. Primary Endpoint

Thirty days after the administration of the MenACYW conjugate vaccine (approximately 5 years after priming as toddlers), the sufficiency of the percentages of participants in Group 1 who achieve an hSBA vaccine seroresponse (see definition below) for meningococcal serogroups A, C, W, and Y will be tested.

Seroresponse will be considered sufficient if lower limit of the 1-sided 97.5% CI calculated using the Exact method (Clopper-Pearson method) for percentage of participants with hSBA seroresponse against serogroups A, C, W and Y is greater than 75%.

This is equivalent to testing $H_0: p \leq 0.75$ against $H_1: p > 0.75$, where p is the observed proportion of subjects with hSBA seroresponse against serogroups A, C, W and Y. The CI for the single proportion will be calculated using the exact method (Clopper-Pearson method).

Note: hSBA vaccine seroresponse for serogroups A, C, W, and Y is defined as:

- For a subject with a pre-vaccination titer < 1:8, the post-vaccination titer must be $\geq 1:16$
- For a subject with a pre-vaccination titer $\geq 1:8$, the post-vaccination titer must be at least 4-fold greater than the pre-vaccination titer

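### The SAP makes the FAS analysis of booster response conditional on attrition above 10%, although the protocol requires it unconditionally, and it declares no change

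*SAP*

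**What the plan says.** Protocol 9.4.1 sets one rule for immunogenicity: "All immunogenicity analyses will be performed on the PPAS and on the FAS". It attaches no condition, and no 10% threshold appears anywhere in the protocol. The opening of protocol section 9 says the SAP is to be written in accordance with the protocol.

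SAP 1.3 assigns sets differently. The response to the Group 1 dose at V1 is described on PPAS1, "and on FAS1 if the attrition rate from FAS1 to PPAS1 is greater than 10" per cent. The response to the Year 5 dose is described on PPAS2, "and on FAS2 if the attrition rate from FAS2 to PPAS2 is greater than 10" per cent.

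FAS1 is already limited to vaccinated participants who "had a valid post-vaccination serology result (hSBA or rSBA accordingly) 5 years after priming vaccination at V1" (Group 1). One of the PPAS exclusions is a judgement item covering other deviations that affected the immune response, "as determined by the clinical team before locking the database".

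The primary criterion in SAP 1.4.2 begins: "Seroresponse will be considered sufficient if lower limit of the 1-sided 97.5% CI calculated using the Exact method (Clopper-Pearson method"; the limit must exceed 75%. Neither that section nor protocol 9.4.2 names the analysis set for the test. SAP section 5, which is the place for changes to planned analyses, is marked as not applicable.

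**The concern.** The protocol commits to two analyses of each booster response. The SAP commits to one, and to the second only if a threshold is crossed. That removes a promised analysis rather than adding technical detail, and the SAP does not declare it.

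The rule also appears to reach the primary endpoint. The SAP 1.3 bullet speaks of describing the immune response, but it stands under the general instruction on where immunogenicity analyses are performed, and it covers the V1 dose in Group 1. That is the dose whose response is tested. This is an inference. If it is wrong, the SAP gives the primary test no analysis set at all.

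The study is uncontrolled (protocol 6.3.2: "This is an open-label study"), and its only formal claim compares a single proportion with 75%. The FAS result is how a reader sees whether the exclusions mattered. Under the SAP, up to 10% of vaccinated and assayed children could be left out of the only reported result: 8 of 84, or 25 of 250.

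**Working it through.** **Inputs.** SAP 1.2 gives a null proportion of 0.75, a one-sided exact test at 0.025, and assumed seroresponse of 0.95 (A and Y), 0.90 (C) and 0.925 (W). It gives n = 84 for the stated power and about 250 per group as a maximum. SAP 1.3 gives the 10% trigger.

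**Reproducing the plan's power.** The criterion is met at the smallest count r with P(X ≥ r | n, 0.75) ≤ 0.025. For n = 84, r = 72: 72/84 has a Clopper-Pearson lower limit of 0.7638, while 71/84 gives 0.7499 and fails. P(X ≥ 72) is then 99.97% at 0.95, 92.59% at 0.90 and 99.03% at 0.925. The product over the four serogroups is 91.6%. All agree with SAP Table 3.1 ("A sample size of 84 achieves at least 90.0% power"), and none depends on the FAS condition.

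**How many can be excluded without triggering the FAS.** The SAP requires attrition greater than 10%. At FAS1 = 84, 8 exclusions are 8/84 = 9.5%, which does not trigger. At FAS1 = 250, 25 exclusions are exactly 10.0%, which also does not trigger.

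**Worst case at 250.** With 25 excluded, PPAS1 = 225 and passes at 182/225 (80.9%). If all 25 were non-responders, FAS1 would be 182/250 (72.8%), lower limit 66.8%, and would fail, because it needs 202/250. Even with all 25 failing, FAS1 passes once PPAS1 reaches 202/225 (89.8%).

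**Chance of a split result.** Let X ~ Bin(n, p) be responders in the PPAS and Y ~ Bin(k, pe) responders among the k excluded, independent, with N = n + k. Let c(·) be the critical count. Then

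P(PPAS passes, FAS fails) = P(X ≥ c(n) and X + Y < c(N)),

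and the reverse split is P(X < c(n) and X + Y ≥ c(N)).

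Assumptions: pe = 0.75 (not in the documents), FAS sizes other than about 250, and exclusions at or just under 10%.

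| FAS N (excluded k) | c(n) of n | c(N) of N | C, p = 0.90 | W, p = 0.925 | A or Y, p = 0.95 |
|---|---|---|---|---|---|
| 84 (8) | 65 of 76 | 72 of 84 | 8.64% | 2.95% | 0.353% |
| 93 (9) | 72 of 84 | 79 of 93 | 4.41% | 1.30% | 0.113% |
| 120 (12) | 91 of 108 | 100 of 120 | 1.55% | 0.20% | 0.0048% |
| 150 (15) | 112 of 135 | 124 of 150 | 0.83% | 0.043% | 0.0003% |
| 250 (25) | 182 of 225 | 202 of 250 | 0.011% | below 0.0001% | below 0.0001% |

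The last three columns give the chance, per serogroup, that the PPAS passes and the FAS fails. For serogroup C the reverse split at pe = 0.75 is 0.37%, 1.21%, 0.51%, 0.06% and 0.0002%, in the same row order.

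**If excluded children respond like the rest** (p = pe = 0.90, serogroup C):

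| FAS N | PPAS passes, FAS fails | PPAS fails, FAS passes |
|---|---|---|
| 84 | 1.55% | 1.57% |
| 93 | 0.39% | 3.50% |
| 120 | 0.07% | 1.39% |
| 150 | 0.03% | 0.23% |
| 250 | 0.0001% | 0.0009% |

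Under this assumption, reporting the PPAS alone does not favour success.

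**The case against.** The strongest reply is that little turns on this. The trigger is pre-specified, does not look at seroresponse, and brings the FAS back when the sets differ by more than 10%. At about 250 children the chance of a misleading split is negligible. The 8.6% figure needs FAS1 as small as 84, the maximum untriggered exclusions, and excluded children responding at the null value. All of that stands, and it limits the size of the point.

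The condition also excludes nobody: both documents remove the same children from the PPAS, and the SAP drops only the companion analysis. The endpoint is a laboratory titre, and the judgement exclusions must be made before database lock. The documents give no indication of how many exclusions would come from that item. These points weigh against any suggestion of selective exclusion, and none is made here.

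It can further be said that protocol 9.4 calls itself a summary, and that 9.4.1 cannot be applied literally because no per-protocol set is defined for persistence. That softens the mismatch but does not remove it. For the booster response both sets are defined, and making a promised analysis conditional is more than elaboration.

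Finally, the link to the primary test is inferred. Either reading needs repair: the condition governs the test, or the test has no named set.

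**Conclusion.** The concern holds. For both booster responses the SAP makes conditional what the protocol requires outright, and section 5 of the SAP does not say so. With attrition of 10% or less, the FAS1 and FAS2 results would not be produced under the SAP.

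This should be corrected, but it does not threaten the primary conclusion at the planned size: the decision rule and the stated power are unaffected. The effect becomes noticeable only if the evaluable number falls towards 84. Those split probabilities rest on assumed FAS sizes, an assumed response among excluded children, and independence between excluded and retained children.

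**What to change.** In SAP 1.3, delete both attrition conditions and always report FAS1 and FAS2 beside PPAS1 and PPAS2. In SAP 1.4.2, name PPAS1 (the set SAP 1.3 always uses) as the set for the primary sufficiency test, with FAS1 reported beside it.

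Settle the wording before the interim database lock described in SAP 1.5. If that lock has passed, add the FAS1 results and record the departure in SAP section 5.

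Declaring and justifying the condition in section 5, or amending protocol 9.4.1, would also reconcile the texts, but the reader would still lose the FAS result at low attrition. The same edit could record two other departures from protocol 9.4.1: SAP 1.3 puts persistence on FAS3 and FAS4 only, and SAP 1.4.3 puts the sex subgroups on the PPAS only.

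The cost is SAP wording and one extra run of existing table programs, with no new data.
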